The second primary outcome in this study is pain self-efficacy. Pain self-efficacy is defined as “a belief in one’s ability to carry out activities even when in pain” (Nicholas et al., 2015, p. 153). Pain self-efficacy will be measured using the PSEQ-10 (Nicholas, 2007). The PSEQ-10 is a ten-item scale scored as a total (0-60). The PSEQ-10 includes ten statements where participants are asked to rate, from zero to six, how confident they are that they can do certain things despite their pain (Nicholas, 2007). The PSEQ is grounded in Bandura’s concept of self-efficacy and has been frequently used in MSKP research (Dube et al., 2021; Nicholas, 2007). The PSEQ-10 was judged to have good content validity, structural validity, test-retest reliability and responsiveness whilst its internal consistency was judged as excellent in the COSMIN guided systematic review conducted by Dube et al. (2021). Furthermore, the PSEQ was recommended as the most appropriate PROM for measuring pain self-efficacy in Slijser-Koehorst et al.’s Delphi-study (2019). The PSEQ-10 has been cross-culturally adapted to Danish in a chronic LBP population and a Swedish cross-cultural adaptation of the PSEQ-2 in a MSKP population has been recently published (Ekhammar et al., 2024; Vejlgaard et al., 2021). The MCID for the PSEQ-10 has previously been cited to range from 5.5-8.5 (Dube et al., 2021). The PSEQ-10’s standard error of the mean (SEM) has been cited to range from 1.23 to 5.66 and the minimal detectable change cited as 11.52 (Dube et al., 2021). Pain self-efficacy has been chosen as a primary outcome in this study as it has the potential to change rapidly in response to an educational intervention, is thought to mediate the relationship between pain and disability and because higher pain self-efficacy is thought to be protective of the development of chronic MSKP (Lee et al., 2015; Martinez-Calderon et al., 2018; Miles et al., 2011).

Secondary outcome measures

- Secondary outcome PROMs

Secondary outcome measure PROMs will be collected and analysed as mean aggregate change from baseline to 24-72 hours prior to the initial physiotherapy consultation, 24 hours

post-initial physiotherapy consultation and at three months post-baseline. Between group differences in changes over time will also be analysed.

- *Secondary analyses of primary outcome measures*

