This statistical analysis plan is part of the PainSMART-project which is a collective suite of studies utilising mixed methods. The PainSMART-project was initiated in 2021 with the aim of improving early musculoskeletal pain (MSKP) management through patient-centered MSKP education based on modern pain science. The PainSMART project's motivation is the high burden of MSKP and the issues encountered within primary care clinical practice associated with the persistence of misconceptions surrounding MSKP. The PainSMART-project has to date conducted pilot-studies within the primary care setting that have led to the development of the seven-minute-long digital educational film entitled 'Be PainSMART:er' (hereafter known simply as 'the film'). The film forms the basis for the implementation of a two-stage PainSMART-strategy which consists of exposure to the film prior to the initial physiotherapy consultation and a discussion based on the film between the patient and the physiotherapist at the initial physiotherapy consultation. The aim of this study is to scientifically evaluate the effects of adding the PainSMART-strategy to the current MSKP primary care physiotherapy care pathway in the Swedish healthcare regions of Östergötland (RÖ) and Jönköping (RJL).

Description of specific objectives or hypotheses

The objective of the PainSMART-project is to evaluate the effects of administering the PainSMART-strategy as an adjunct to usual physiotherapy management compared to usual physiotherapy management alone.

Research hypotheses for confirmatory research questions

1. Exposure to the PainSMART-strategy as an adjunct to usual physiotherapy management improves the following outcomes significantly more than usual physiotherapy management alone for patients with MSKP (* = primary outcomes) (H1)

- Reduction in pain intensity*.
- Higher pain self-efficacy*.
- Lower MSKP illness perceptions.
- Higher levels of reassurance of the benign nature of MSKP.
- More adaptive MSKP coping and psychological flexibility.
- Higher self-reported levels of physical activity.
- More positive global ratings of change.
- Lower number of healthcare visits, referrals for diagnostic imaging and to specialist/tertiary care for MSKP, lower analgesic medication use, fewer sick leave days and lower direct costs.

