 - Between group mean change over time from baseline to three months post-baseline (primary time point two)

Secondary outcomes

Patient reported outcome measures (PROMS)

-Pain intensity

Self-reported average pain intensity, worst pain intensity and best pain intensity in the previous 24 hours will be measured using numerical rating scales (NRS). Score range: 0-10 with 0 = no pain and 10 = worst imaginable pain.

- Time Frame: collected at baseline, 24-72 hours prior to the initial physiotherapy consultation, 24 hours post initial physiotherapy consultation and at three months post-baseline.
- Calculation to derive outcome:
 - Within group mean change in average pain intensity over time from baseline to follow-up three months post-baseline (all time points).
 - Between group mean change in average pain intensity over time from baseline to 24 -72 hours prior to the initial physiotherapy consultation.
 - Within and between group mean change in worst pain intensity total score over time from baseline to follow-up three months post-baseline (all time points).
 - Within and between group mean change in best pain intensity total score over time from baseline to follow-up three months post-baseline (all time points).

-Pain self-efficacy

Self-reported pain self-efficacy will be measured using the Pain Self-efficacy Questionnaire 10 (PSEQ-10). The PSEQ-10 is a 10-item questionnaire. Score range: 0-60, a higher score indicating greater pain self-efficacy.

- Time Frame: collected at baseline, 24 -72 hours prior to the initial physiotherapy consultation, 24 hours post initial physiotherapy consultation and at three months post-baseline.
- Calculation to derive outcome:
 - Within group mean change over time from baseline to follow-up three months post-baseline (all time points).
 - Between group mean change over time from baseline to 24 -72 hours prior to the initial physiotherapy consultation.

-Musculoskeletal pain (MSKP) illness perceptions

MSKP illness perceptions will be measured using the Brief Illness Perception Questionnaire (BIPQ). The BIPQ is a nine-item questionnaire where eight items are scored on a 11-point

NRS with anchor statements (score range 0-80, higher score reflecting higher perceived threat). One item is a free text question regarding believed cause of the MSKP (causal item).

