An internal pilot interim analysis was planned and conducted after 50% of the sample had reported outcomes at time point 2 (pre physiotherapy consultation) and 3 (primary time point one, post initial physiotherapy consultation). This to evaluate the viability of the a-priori sample size calculation and the recruitment frequency. The analysis utilised linear mixed models to investigate between group difference (effect size) for change from baseline to time points 2 and 3 in outcome. The significance level for the interim analysis was $p=0.05$. After interim sample size calculation, the sample size was slightly adjusted when taking loss to follow-up into account. The sample size calculation is described in the trial protocol. The trial would have been stopped if the internal pilot interim analysis could not be performed due to not attaining 50% of the sample size at Time point 2 and 3 within 6 months. No further interim analyses are planned.

Final analysis

The trial is planned to finish recruitment of new patient participants in Dec 2024 – Jan 2025. The final three-month follow-up data collection will therefore be in Mar - Apr 2025. All outcomes will be analysed collectively.

Analysis methods

Primary outcome analysis

-Pain intensity and Pain self-efficacy

Hypothesis testing for the two primary outcomes *pain intensity* and *pain self-efficacy* (score on average pain NRS in the last 24 hours and PSEQ-10) will be based on analysis of group mean change from baseline. Baseline scores and group mean change in primary outcome scores from baseline to primary time points one and two for the intervention and control groups and the between-group change for these time points will be presented as means and CI. The within and between-group change on primary outcomes from baseline to 24 hours post initial physiotherapy consultation and three months post-baseline will be analysed according to ITT principles using a maximum likelihood approach for mixed models adjusted for a relevant covariance structure. The models will be adjusted for baseline covariates where relevant. Baseline factors that will be analysed for potential covariate adjustment include: age, sex, educational level, employment, pain duration, number of pain sites, comorbidities, days to initial physiotherapy consultation, previous healthcare interventions, ÖMPSQ risk category, self-reported sick leave and analgesic medication consumption.

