Baseline factors that will be analysed for potential covariate adjustment include: age, sex, educational level, employment, pain duration, number of pain sites, comorbidities, days to initial physiotherapy consultation, previous health care interventions, ÖMPSQ risk category, self-reported sick leave and analgesic medication consumption. Between-group differences on outcomes from baseline to 24-72 hours prior to the initial physiotherapy consultation, 24 hours post the initial physiotherapy consultation and three months post-baseline will be analysed.

Complier average causal effect (CACE) analysis

CACE estimation will be implemented in a structural equation modeling program (eg Mplus) using a maximum likelihood approach. As displayed in the following Directed Acyclic Graph (DAG) model (Figure 1), the covariate (X = baseline score for observed outcome variable) predicting both the outcome (Y = Follow-up score of observed outcome variable) and compliance status (C = dichotomous adherence latent class variable).

[figure not shown]

Figure 1. Directed Acyclic Graph (DAG) for CACE analysis

Solid lines from the square boxes for observed variables indicate regressions among these variables. For example, the path from Z (a binary treatment variable) to Y (the outcome) illustrates the treatment effect. The dashed lines originating from the latent class variable C to the regression of observed variables (Z, X) on the outcome suggest that the effects on the outcome can differ across compliance classes. The solid line from the latent class variable to the outcome shows that the means for noncompliers and compliers can differ. The model will be adjusted for other baseline covariates where relevant. Baseline factors that will be analysed for potential covariate adjustment include: age, sex, educational level, employment, pain duration, number of pain sites, comorbidities, days to initial physiotherapy consultation, previous health care interventions, ÖMPSQ risk category, self-reported sick leave and analgesic medication consumption. Between-group differences on outcomes from baseline to 24-72 hours prior to the initial physiotherapy consultation, 24 hours post initial physiotherapy consultation and three months post-baseline will be analysed (Hesser, 2020).

Responder analysis

Responder analyses for the primary and secondary outcomes will be based on calculation of the trial specific MCIDs. The sample of the patients for the responder analyses will be as follows:

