- Intervention group:
 - Responders: patients attaining within group mean change equal to and above the study specific threshold for MCID.
 - Non-responders: patients attaining within group mean change below the study specific threshold for MCID.
- Control group:
 - Responders: patients attaining within group mean change equal to and above the study specific threshold for MCID.
 - Non-responders : patients attaining within group mean change below the study specific threshold for MCID.

The group comparison refers to the difference in responder rates between the intervention and the control group using Chi-square test for independence.

Mediation analysis

The planned mediation analysis of the PainSMART-study will help analyse the causal mechanisms of the PainSMART-strategy. If the PainSMART-strategy is found to be effective, the causal mediation analysis will help explain how the strategy works. Conversely, if the strategy is not found to be effective, the causal mediation analysis will help identify where the hypothesised mechanisms broke down.

Primary mediation objective

The primary objective is to confirm if improvement in hypothesised mediators, MSKP illness perceptions and reassurance of the benign nature of MSKP, mediate the effect of the PainSMART-strategy on pain intensity and pain self-efficacy.

Rationale for the hypothesised mediators

MSKP illness perceptions and level of reassurance as to the benign nature of MSKP are hypothesized, based on an integration of the CSM and concept of self-efficacy, to be potential mediators of the effect of the PainSMART-strategy on pain intensity as well as other secondary outcomes. The integrated model also hypothesizes pain self-efficacy to be a mediator in a series of mediators of the PainSMART-strategy's effects. The theoretical rationale underlying the hypothesised mediators in the PainSMART-strategy are explained in full in the trial protocol.

Outcomes

Primary outcomes are average pain intensity in the previous 24 hours measured with a 11-point NRS and pain self-efficacy measured with PSEQ-10. Hypothesised mediators are MSKP illness perceptions measured with the BIPQ and level of reassurance as to the benign nature of MSKP measured with a 11-point NRS.

Data collection

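### The responder rule gives no direction and classifies by a group mean, and the unadjusted chi-square test ignores the baseline score on which reaching a change threshold depends

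*SAP*

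**What the plan says.** The SAP, under Sensitivity analyses (Responder analysis), sets the scope: "Responder analyses for the primary and secondary outcomes will be based on calculation of the trial specific MCIDs". In both arms, responders are "patients attaining within group mean change equal to and above the study specific threshold for MCID" and non-responders are "patients attaining within group mean change below the study specific threshold for MCID". Responder rates are then compared between arms "using Chi-square test for independence", with no covariate.

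The threshold is trial-specific. Under Primary and Secondary outcome analysis it is a ROC/Youden cut-off for change, anchored on a global rating of change of 1 to 5 (improved) against -5 to 0 (not improved).

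On direction, the SAP's hypotheses list "Reduction in pain intensity" as the pain benefit, and BIPQ has "score range 0-80, higher score reflecting higher perceived threat". For PSEQ-10, reassurance and both BPCI-2 subscales, higher is better. No favourable direction is stated for sitting time. Hypothesis testing "will be based on analysis of group mean change from baseline", and the order of subtraction is not given.

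The Protocol (Secondary analyses of primary outcome measures) makes the proportion of responders a secondary outcome for both primary measures. Protocol Table 1 sets no minimum pain score and no maximum PSEQ-10 score for entry.

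**The concern.** Three things in the rule need attention.

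- **Unit.** A within-group mean change is one number per arm. Taken literally, it makes a whole arm responders or non-responders and leaves nothing for a chi-square test. The individual patient's change must be meant.
- **Direction.** No single order of subtraction suits both primary outcomes. Follow-up minus baseline makes the at-or-above rule wrong for pain and BIPQ. Baseline minus follow-up makes it wrong for PSEQ-10. It works for both only if change is coded as improvement outcome by outcome, which the SAP does not say.
- **Test.** A patient who starts with little pain or high self-efficacy has less room to change by a fixed amount, and entry does not exclude such patients. Baseline score is therefore a strong predictor of response, it is already collected, and the test ignores it.

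At stake is how a secondary outcome reads in a trial whose null hypothesis refers to clinical as well as statistical differences. If the coding is settled only at analysis, the responder result can be questioned whichever way it falls.

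**Working it through.** The documents state no responder rate, responder difference or responder power, so there is no plan figure to reproduce.

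**1. Effect of the direction gap (pain NRS)**

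Inputs:
- Difference 2 points, SD 4 (Protocol, Sample size), with the SD taken here as that of change.
- Threshold 2 points (the pain MCID cited in the Protocol, standing in for the trial's own).
- Control mean change 0 (assumed).

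Let D be follow-up minus baseline, normal, with mean 0 in control and -2 in the intervention arm.

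- Improvement coding, P(D ≤ -2): control Φ(-2/4) = Φ(-0.5) = 30.9%; intervention Φ(0/4) = 50.0%. Difference **+19.1 points**.
- Literal, threshold +2, P(D ≥ 2): control 1 - Φ(0.5) = 30.9%; intervention 1 - Φ(4/4) = 15.9%. Difference **-15.0 points**.
- Literal, threshold signed as -2, P(D ≥ -2): control 1 - Φ(-0.5) = 69.1%; intervention 1 - Φ(0) = 50.0%. Difference **-19.1 points**.

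With control mean change from 0 to -2 and SD 2.5 or 4, improvement coding gives +19 to +31 points and the literal +2 reading gives -5 to -16 points.

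**2. Cost of ignoring baseline**

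This was simulated with 204 per arm (408/2, from Protocol, Sample size), a two-sided 5% level, response correctly coded as individual improvement, 3,000 replicates, and scores rounded and held within the scale. All distributional inputs are assumed:
- NRS: baseline mean 5, SD 2; mean improvement before truncation 1.0 (control) v 1.6 (intervention); threshold 2.
- PSEQ-10: baseline mean 40, SD 12; mean improvement 3 v 6; threshold 5.5, the low end of the Protocol's statement that "The MCID for the PSEQ-10 has previously been cited to range from 5.5-8.5".

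| Outcome | Baseline–follow-up correlation | Correlation of baseline with response | Power, chi-square | Power, logistic on arm and baseline |
|---|---|---|---|---|
| NRS | 0.3 | 0.48 | 54.0% | 64.3% |
| NRS | 0.5 | 0.42 | 65.1% | 73.0% |
| NRS | 0.7 | 0.34 | 85.3% | 89.2% |
| PSEQ-10 | 0.3 | -0.51 | 36.6% | 46.1% |
| PSEQ-10 | 0.5 | -0.45 | 47.2% | 55.7% |
| PSEQ-10 | 0.7 | -0.38 | 67.0% | 73.1% |

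Other assumed baselines (NRS mean 4, SD 2.5 and mean 6, SD 2; PSEQ-10 mean 45, SD 10) gave gains of 2 to 11 points. The smallest gain came where chi-square power was already 87%. A further set of assumed baselines and effects, over the same correlations, gave about 3 to 13 points. With no treatment effect, both tests rejected in 4.0% to 5.6% of runs, so the gain does not come from an inflated error rate.

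**3. Consistency with the rest of the SAP**

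The SAP analyses its other dichotomous secondary outcomes with generalised linear mixed models reported as odds ratios with CIs, and it allows baseline covariates in its continuous models. The responder comparison is the exception.

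**The case against.** The strongest reply is that the direction is left unsaid, not stated wrongly. The Protocol gives the pain MCID as an unsigned two points and speaks of the magnitude of change, and the SAP's cut-off is anchored on patients who rate themselves improved. All of this points to improvement coding, under which the rule is correct for every outcome. This stands. A reader might infer that the plan will count worsened patients as responders and report wrong rates. The documents do not support that, because they give no negative threshold and no order of subtraction. The reversed figures show what an unstated convention could do, not what the plan will produce.

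Second, an unadjusted comparison of proportions is valid in a randomised trial, and an odds ratio is not the planned difference in responder rates. Both points are right. The cost is therefore power only, and the fix must keep the difference in rates.

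Third, a reader might infer that patients already near the best score dilute the result by a known amount. That cannot be established: the documents give no baseline distribution, and the trial's MCIDs are still to be estimated. Under assumed baselines and the cited MCIDs, the share without room is anywhere from 1% to 16% for pain and 3% to 29% for PSEQ-10. Randomisation should spread these patients evenly, so they favour neither arm. A subset restricted to patients with one MCID of room is not recommended, because its cut-off would be estimated from follow-up data.

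**Conclusion.** The point holds in two parts of different weight. The unit and direction are mainly a wording repair: improvement coding is the likely intent, and the comparison reverses only under a literal signed reading (from +19 to -15 or -19 points at a 2-point benefit, SD 4 and control change 0). The unadjusted test is a substantive but modest loss, roughly 2 to 13 points of power with 204 per arm. That range rests on assumed baselines, effects and baseline–follow-up correlations of 0.3 to 0.7. There is no bias between arms. The primary mixed-model analysis of continuous change is untouched; only a secondary or sensitivity analysis is affected.

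**What to change.** Rewrite the responder definition in the SAP:

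- A responder is an individual patient whose own improvement is at least the trial-specific MCID for that outcome and time point.
- Improvement is baseline minus follow-up for pain NRS and BIPQ, and follow-up minus baseline for PSEQ-10, reassurance and the BPCI-2 subscales. State the favourable direction for the physical activity items, sitting time in particular.
- Derive the ROC cut-off on the same improvement-coded change.

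Replace the chi-square test with logistic regression on arm and the baseline score of that outcome. Report the odds ratio and, to keep the planned estimand, the baseline-standardised difference in responder rates, each with a CI. The standardised difference is the average predicted response with every patient set to intervention, minus the same with every patient set to control.

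The cost is a few lines of SAP text and slightly more analysis work. No new data are needed, and the SAP already allows R if SPSS does not give the standardised difference conveniently. The change should be dated and made before outcomes are analysed by arm.

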NRS pain intensity and pain self-efficacy will be additionally analysed as secondary outcomes for within group and between group differences for data collected at non-primary outcome time points. In addition to the primary outcome of average pain intensity, worst pain intensity and best pain intensity in the previous 24 hours will be measured using two NRS scales (0-11 from 0 = no pain to 10 = worst imaginable pain) (Jensen et al., 1999). Both primary outcome measures will be additionally analysed as a secondary outcome for proportion of responders based on study specific MCIDs. The MCIDs for the two primary outcomes will be calculated for interpretation of the within and between-group differences. The MCIDs will be calculated for the whole cohort using an anchor method based on the Global rating of change scale (GRoCs) scores (Revicki et al, 2008).

- *MSKP illness perceptions*

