on generalisability (Mercieca-Bebber et al., 2018). All outcome data will be compared based on the ITT principle. This means that all patients that have been randomised remain in the analysis based on their group allocation. In the event of substantial missing data, evaluation of the mechanisms for missing data will be used (Enders, 2011). Missing data will otherwise be handled under the missing at random assumption (Enders, 2011). Multiple Imputation or Maximum Likelihood estimation will be used assuming that missing data is conditional on variables included in the model. Imputation method considering missing at random or not missing at random will be used in the ITT analysis. Patients who cancel their initial physiotherapy consultation will be excluded from the PREM analysis but will remain in the study for PROM and healthcare register data analyses.

Study monitoring and harms

There will be no data monitoring committee since the study is independent from the sponsor and the intervention is implemented as an adjunct to usual physiotherapy management with low risk for unexpected adverse events. The PROMs included in the study are sensitive to worsening in the patients' condition. An internal pilot interim analysis was planned and conducted (February 29th, 2024) after approximately 50% of the initially planned sample (n = 229) had consented to the study and reported outcomes at time point two (72-24 hours prior to the initial physiotherapy consultation) and three (24 hours post the initial physiotherapy consultation). This interim analysis enabled evaluation of the viability of the a-priori sample size calculation and the recruitment frequency. The analysis utilised linear mixed models to investigate between group differences (effect size) for change from baseline to time points two and three for outcome. The significance level for the interim analysis was p=0.05. After interim sample size calculation, the sample size was adjusted slightly to take loss to follow-up into account. The sample size calculation is described under the protocol heading sample size. The trial would have been stopped if the internal pilot interim analysis could not be performed due to not attaining 50% of the sample size at Time point two and three within six months. No further interim analyses are planned.

Ancillary and post-trial care

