Patients receive seven questions and physiotherapists 3 questions regarding their experience of the initial physiotherapy consultation. Between group mean difference for responses to these questions will be analysed using independent sample t-tests. These analyses will be presented as mean and SD for each group and the between group difference in mean and CI. Three of the patient questions will be analysed for concordance with the matched physiotherapists' questions. Concordance within the intervention group and control group will primarily be analyzed by calculating intraclass correlation coefficient (ICC) with 95% confidence interval on each question as well as all three questions combined. Two-way random effects model will be used for ICC, assuming raters to be randomly selected. The ratings are single measures analyzed for consistency, to measure systematic differences between ratings. Patients and physiotherapists are treated as two independent raters, rating each of the three questions.

Sensitivity analyses

The following are all re-analyses of the primary and secondary outcomes under different conditions:

- Per-protocol analysis
- Complier average causal effect (CACE) analysis
- Responder analysis
- Complete case analysis (in case of >5% missing data)

Per-protocol analysis

Per-protocol analyses for the primary and secondary outcomes will be conducted to assess robustness of the ITT analyses and to further inform decisions regarding superiority. The sample of the patients for the per-protocol analyses will be as follows:

- Intervention group: patients receiving the PainSMART-strategy with no or minor deviation from protocol.
- Control group: patients receiving intervention with no or minor deviation from protocol.

Data on the physiotherapists' self-reported adherence to the protocol will be cross-referenced with the intervention respective control group patient consultations that each physiotherapist has conducted. This, in combination with the intervention group patients' self-reported exposure to the film, will provide data on deviation from protocol.

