The relationships that will be estimated for each mediator on each outcome are described in the primary mediation analyses, see “Mediation analyses”. The mediator models will be adjusted for the baseline score in the dependent variable (outcome), the mediator as well as the potential pre-treatment confounders. The interaction term between the intervention allocation and the mediator will be analysed to examine its impact on the indirect effects. The interaction term will be adjusted for in the outcome model if indicated. Missing data will be handled using full information maximum likelihood in the mediation analyses, if other methods are not indicated. The effects will be reported with 95% CI.

Predictors and sub-groups

-Baseline predictive factors

All baseline factors will be explored as potential predictors for health outcomes at time point 4 for the PainSMART intervention group cohort and also for the entire cohort. Regression based statistics will be used. Prediction models will be constructed exploring predictive performance. Internal and external validation of the models will be explored.

-Moderator analyses

Moderator analyses are planned based on the ÖMPSQ risk group categories. The two sub-groups are defined as high risk (score >50) and low risk (score ≤ 50) for persisting disability and work absence. The dependent variable is the intervention’s effect on health outcomes at time points 3 and 4.

Missing data

Proportion of missing and available data will be investigated through completion rate for each outcome measure and at all data collection time points. The proportion and patterns of missing data in outcomes will be assessed if missing data is $>5\%$. Comparison of characteristics and baseline score on PROMs between participants with and without missing data at one or several data collection time points or according to specific missing data patterns will be analysed to interpret the potential impact of missing data on generalizability.

Imputation will be conducted and handled under the missing at random assumption. In the event of substantial missing data, an evaluation of the mechanisms for missing data will be conducted (Enders, 2011). Multiple Imputation or Restricted Maximum Likelihood estimation will be used assuming that missing data is conditional on variables included in the model. Other imputation methods may be used if necessary.

[Statistical software](#)

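### Responder rates are compared by an unadjusted chi-square test with no stated effect measure or interval; adjusting for the baseline score would be more precise at almost no cost

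*SAP*

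**What the plan says.** The SAP, under Sensitivity analyses, Responder analysis, uses the same definition in each arm: "Responders: patients attaining within group mean change equal to and above the study specific threshold for MCID". Patients below the threshold are non-responders. The comparison is then: "The group comparison refers to the difference in responder rates between the intervention and the control group using Chi-square test for independence". That section gives no covariate, no effect measure with an interval, and no rule for a patient whose follow-up score is missing.

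The documents give the analysis two labels. In the protocol, under Secondary analyses of primary outcome measures: "Both primary outcome measures will be additionally analysed as a secondary outcome for proportion of responders based on study specific MCIDs". The SAP lists it among sensitivity analyses, introduced by: "The following are all re-analyses of the primary and secondary outcomes under different conditions". The protocol's own sections on analysis of primary and of secondary outcomes also place MCID-based analyses among the sensitivity analyses.

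Three other rules bear on the point:

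- SAP, Secondary outcome analysis, Categorical variables: the other dichotomous secondary outcomes, including the dichotomised global rating of change, get generalised linear mixed models, with between-group results as odds ratio and CI.
- Protocol, Missing data: under ITT, "all patients that have been randomised remain in the analysis based on their group allocation".
- SAP, Missing data: "Multiple Imputation or Restricted Maximum Likelihood estimation will be used assuming that missing data is conditional on variables included in the model".

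**The concern.** A responder is defined by change from baseline reaching a cut-off. A patient who starts at 2 on the 0-10 pain scale can fall by 2 points only by reaching zero; a patient who starts at 8 has far more room, and regression to the mean helps as well. Baseline therefore explains much of who becomes a responder. It is collected on every analysable patient, because change cannot be computed without it. The chi-square test makes no further use of it.

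At stake is the precision of a named secondary outcome, and whether it will be reported as an estimate with an interval or only as a p-value. The responder comparison is one of the ways the trial will judge clinical relevance, which its null hypothesis mentions explicitly. It is also the one dichotomous secondary outcome handled differently from the rest.

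**Working it through.** **No figure to reproduce.** The documents give no expected responder rate, power or sample size for this analysis, so the size of the gain has to be illustrated under assumptions.

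**From the documents:** 1:1 allocation and a follow-up target of 408 (protocol, Trial design and Sample size), so 408/2 = 204 per arm. The protocol's literature MCID for pain is 2 points.

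**Assumed:** pain SD 2.2 at both times; mean fall of 1 point in controls and 1.6 in the intervention arm (true effect 0.6); baseline to follow-up correlation ρ = 0.3, 0.5 or 0.7; normal scores; two-sided 0.05; no missing data. Responder status is taken as the individual patient's change reaching 2 points.

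**Step 1. How far change depends on baseline.** With equal SDs, SD of change = 2.2 × √(2(1−ρ)), and the correlation of change with baseline is √((1−ρ)/2). For ρ = 0.3, 0.5, 0.7 this correlation is 0.59, 0.50, 0.39. The gain from adjustment should therefore shrink as ρ rises.

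**Step 2. Responder rates and chi-square power by formula.** Control rate = P(Z ≥ (2−1)/SD of change); intervention rate = P(Z ≥ (2−1.6)/SD of change). SE of the difference = √[(p₀(1−p₀) + p₁(1−p₁))/204]. Power ≈ Φ(difference/SE − 1.96).

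| ρ | SD of change | p₀ | p₁ | Difference | SE | Power |
|---|---|---|---|---|---|---|
| 0.3 | 2.60 | 0.350 | 0.439 | 0.088 | 0.048 | 0.45 |
| 0.5 | 2.20 | 0.325 | 0.428 | 0.103 | 0.048 | 0.58 |
| 0.7 | 1.70 | 0.279 | 0.407 | 0.129 | 0.047 | 0.79 |

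**Step 3. Simulation, 3,000 trials per setting.** The unadjusted chi-square was compared with a logistic regression of responder status on arm and baseline score. The adjusted risk difference was obtained by averaging predicted probabilities over all patients under each arm.

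| ρ | SE unadjusted | SE adjusted | Variance cut | SE cut | Power chi-square | Power logistic |
|---|---|---|---|---|---|---|
| 0.3 | 0.0479 | 0.0425 | 21% | 11% | 0.435 | 0.543 |
| 0.5 | 0.0482 | 0.0444 | 15% | 8% | 0.574 | 0.638 |
| 0.7 | 0.0465 | 0.0442 | 10% | 5% | 0.777 | 0.815 |

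The variance cut is 1 − (SE adjusted/SE unadjusted)²; for ρ = 0.5, 1 − (0.0444/0.0482)² = 0.15. The simulated chi-square power agrees with Step 2. The power gains are 10.8, 6.4 and 3.8 points.

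**Step 4. Type I error** (true effect set to 0): chi-square 0.048, 0.052, 0.051; logistic 0.050, 0.050, 0.048. Both are at the nominal level, so the gain is in precision and not in validity.

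**The case against.** The strongest reply is that nothing here is wrong. An unadjusted comparison of proportions in a randomised trial is valid, and change from baseline already uses the baseline score. The SAP and parts of the protocol treat the analysis as a sensitivity check. The study-specific MCIDs are also used directly to interpret the group differences, so the clinical reading does not rest on this test alone. The SAP's Statistical Principles set 95% as the level for confidence intervals in general, so one might be reported anyway. All of this stands, and it limits the point to a free improvement. It does not remove it: the protocol does call the responder proportion a secondary outcome, the other dichotomous secondary outcomes get a model and an interval, and subtracting the baseline score is not the same as adjusting for it.

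A reader might go further and infer that a chi-square test must drop patients without follow-up, so that the comparison is not ITT and is biased by dropout. The documents do not support this. The responder section does not say that only observed cases are used. The protocol applies ITT to all outcome data, the SAP foresees imputation, and complete-case analysis is a separate item in the same list of sensitivity analyses. What can be said is narrower. The section does not state how missing responder status is handled, and the likelihood-based mixed models used for the main analyses produce no completed scores from which to derive a status. That is missing detail. Bias would need dropout to depend on pain differently in the two arms, and nothing in the documents suggests that.

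**Conclusion.** The point holds as a precision gain. For a secondary outcome named in the protocol, the SAP specifies an unadjusted test without effect measure or interval, although a strongly prognostic covariate is to hand. Under the stated assumptions, adjustment reduces the variance of the responder difference by roughly 10% to 20% (standard error by about 5% to 11%) and adds about 4 to 11 points of power, with type I error unchanged. These figures depend on the assumed SD, threshold, effect and correlations. The actual threshold will come from the trial's own anchor analysis and may differ. The gain is largest when baseline and follow-up are weakly correlated. The planned test is not in error, and no statement that the plan excludes patients, departs from ITT or is biased by dropout is warranted. Priority is low: desirable, not essential.

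**What to change.** In the SAP's Responder analysis, replace the chi-square comparison with a logistic regression of responder status on arm and baseline score of the measure concerned. Report the standardised difference in responder rates (or the odds ratio) with a 95% CI, and keep the chi-square as a check.

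Where the follow-up score is missing, impute the score by the multiple imputation already foreseen under Missing data, derive responder status from it, and pool the regression estimates, so that the comparison follows the protocol's ITT rule. State whether the MCID cut-off is fixed once for the cohort or re-estimated in each imputed data set. Use one label, secondary or sensitivity, in both documents.

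The cost is a few sentences in the SAP and a little more analysis. No new data are needed, and the sample size does not change.
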